1.0 SPECIFIC STUDY AIMS

Aims

The overall objective of the study is to improve health-related quality of life and the cancer care experience for health care beneficiaries of Unite Here Health (UHH) in Atlantic City, NJ and Chicago, IL after they receive a new diagnosis of cancer or a relapsed or progressive advanced stage of cancer.

The study aims primarily to determine if the intervention improves a patient's health-related quality of life. Secondarily, the study aims to include the effect on the change in patient satisfaction with decision-making and patient activation, change in health care use and advance directive and goals of care documentation as well as end of life outcomes including health care use and total costs of care.

The intervention consists of trained, culturally sensitive community health workers (CHWs) who assist patients and families in identifying and intervening on complications from social determinants of health, understanding and discussing their care goals, engage in proactive symptom assessment, and participate in care delivery closer to and in patients' homes and communities.

Hypothesis

Compared to patients who receive usual oncology care, patients who partner with CHWs are hypothesized to experience improved health-related quality of life. Secondary outcomes are meant to be exploratory however we expect effects on these outcomes in favor of the intervention.

2.0 BACKGROUND AND RATIONALE

Many patients and families served by Unite Here Health express significant challenges with their cancer care. Many describe significant complications from social determinants of health, poor quality of life with difficult decisions, little understanding of the disease context, uncontrolled symptoms, and treatment and clinic visits that are provided at distances far from their residences. Oncology care delivery for vulnerable patients is often fragmented with poor care coordination, patient-provider communication challenges, and centralization of healthcare services that make care delivery and access even more difficult for vulnerable patients. These barriers in the delivery of care can result in disparate cancer outcomes.

The LEAPS intervention extends the spectrum of care up to 12 months post-enrollment (for patients with newly diagnosed, relapsed or progressive disease). The key elements of the intervention address three major challenges faced by vulnerable patient populations: 1) patients and their families who face social and economic challenges experience challenges in communication with their providers regarding their goals of care and understanding their prognosis; 2) patients experience difficulty in expressing their symptoms to their providers; and 3) patients experience challenges attending their clinic and treatment appointments due to financial burden, travel difficulties and/or lack of social support to drive and accompany them to their visits. (See Appendix for Rationale)

The proposed intervention addresses these three critical care elements by training and deploying culturally-sensitive, community-based health care workers who assist patients and families in identifying complications from social determinants of health such as transportation, financial or housing, discussing goals of care and advance care planning, proactively assess cancer-related symptoms with oversight from a UHH nurse, and assist in coordinating care delivery at home through leveraging telephonic discussions and home visits.

3.0 STUDY ENROLLMENT AND PARTICIPANT ELIGIBILITY

3.1 Study Enrollment

Location

Health beneficiaries of UHH newly diagnosed cancer or relapsed or recurrent cancer may be referred by oncology provider clinics who partner with UHH.

Enrollment Procedures

UHH Staff assigned to the program will target potential patients on an ongoing basis using their claims data system. This includes data from a variety of sources including but not limited to Daily Inpatient Reports; referrals from hospital staff, PCPs and Specialists; referrals from other UHH staff such as those working in customer service; and referrals from Union staff and participants. The study staff will review all potential patients with newly diagnosed or recurrent disease no matter the stage or type to determine eligibility for the program. After the site PI and

study staff conduct proper screening (see below section titled “Screening Procedures” for specific details), the program will be explained to patients and patients will then be enrolled in the study.

Screening Procedures

The Site PI and staff will utilize the following claims data system documents and procedures to also screen for patients who fit the inclusion criteria listed in 3.2. Screen failures will not be included in the study data. The PI will keep a record of history and reasons for screen failures; however, any patient information gathered during this process will be destroyed.

Consent Procedures

The study staff will discuss the intervention with the patient, at the first point of contact, after eligibility has been confirmed. The study staff will introduce the program and describe the program aims and objectives. Patients will be provided adequate time to make an informed decision regarding their participation. Patients who refuse participation or have no capacity for decision-making or consent will not be included in the study.

If a patient is interested and consents verbally, he/she will be provided a welcome letter with basic information and contact phone numbers for the project. The patients will be randomized by Stanford biostatistician using a computer-generated ordered list of randomized numbers in each city. For all patients assigned to the LEAPS intervention arm, the community health worker will contact the patient to begin the intervention procedures that include assisting patients with understanding their goals of care, documenting goals of care, proactively assessing symptoms, and coordinating home-based or community-based care delivery. The intervention will be provided in addition to the usual care processes (Intervention details are provided in Appendix B).

3.2 Participant Criteria

Inclusion criteria

1. Newly diagnosed patients with a cancer diagnosis.
2. Patients with any relapse or progressive disease (any cancer diagnosis) as identified by imaging or biopsy and confirmed by physician.
3. The patients must be 18 years or older.
4. Patients must have the ability to verbally consent and understand study procedures.

Exclusion Criteria

1. Inability to consent to the study.
2. Patients without a newly diagnosed malignancy or patients without relapse of disease.
3. Patients not eligible for fund benefits.

Criteria for Removal from Study

Any patients or families of patients in the intervention arm who withdraw consent will be removed from the study. Upon removal, usual care will be restored for these patients.

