3.3 Enrollment

The target number of subjects at the site is 160 (80 per arm). Patient enrollment will continue until sample size is reached (anticipated 24 months). Data collection will occur at baseline and months 4 and months 12 for each patient in the study. The data follow-up period (to assess utilization) will occur for up to 12 months following each patient enrollment or death (whichever is first).

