4.0 MATERIALS AND METHODS

After a patient is enrolled in the study, the patient will be registered and entered into the project database (CarMa) and assigned an identification number. The identification number will be used on all subject-specific documents and research-related forms.

During registration, patients will be randomized to two arms (Arm A: Usual Care or Arm B: LEAPS Intervention). Specifically, the patients will be randomized 1:1 using a simple randomization strategy in each site into two arms at each site.

All patients, throughout the study, will be asked to complete three surveys: 1) patient health-related quality of life (using Functional Assessment of Cancer Therapy – General (FACT-G) and 2) satisfaction with decision-making (Satisfaction with Decision Scale) and 3) the patient activation measure (Patient Activation Measure-13). A trained study staff member will administer the surveys at baseline (month 0) and again at 4 months and 12 months for patients in the intervention and usual care arm. Participant information will be entered into the CarMa database within 7 calendar days. Study team members will conduct electronic health record chart review of each participant and abstract date of the following: goals of care documented by oncology clinician, advance directive, and Physician Order for Life Sustaining Treatment. All health care claims data will be provided by UHH to the study team for each participant in the study at the study end which will consist of all charges and paid claims for total costs including outpatient, inpatient and pharmacy services. All study team members will be blinded to the randomization assignment. Only the community health workers will know the study assignment and the local site coordinator at each site.

As part of usual care, study PI and team members redesigned benefits such that any member of UHH with cancer will also receive waived copays if they choose to seek care at the preferred

provider in Atlantic City. We will also provide each member with access to transportation and other services to receive care at the preferred provider.

- Arm A: Usual Care (Control) / No Intervention

Patients in this arm receive “usual” care coordination from their care coordination team which includes case management by a registered nurse practitioner to address financial concerns, care navigation and coordination.

- Arm B: LEAPS/ Intervention Group

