The intervention will be comprised of a CHW assignment with a baseline introduction (either telephonic or in-person) of the program followed by a visit (telephonic or in-person) with the community health worker to screen for health-related social needs, identify and refer to community resources for any identified complication from social determinants of health and to begin intervention regarding goals of care and symptom management. All CHWs have undergone standardized training with additional supervised visits to gain skills in engaging patients and families in goals discussion and in symptom assessment algorithms (see Appendix for Details).

The CHW will contact patients based on patients’ ongoing needs but will provide at a minimum weekly support from time to enrollment up to 4 months post-enrollment and then monthly from 4-months post-enrollment until 12-months post-enrollment. The CHW will also conduct meetings with patient’s family and caregivers at the same time intervals where possible. The intervention details are provided in the Appendix.

Lay Health Worker Training

The PI and UHH staff provide ongoing training for the CHWs through formal classroom training (See Appendix for a list of topics covered), biweekly case rounds, shadowing and role plays. All CHWs will also be provided with previously tested and developed standardized training manuals that are refined based on feedback from stakeholders at UHH. The manuals include a highly detailed workflow of the project, from enrollment to completion. CHWs also will receive training on what to say during patient contact, advanced care planning conversations, documentation of advance care planning, the study calendar, data management, and key contact information. CHWs will also receive training on symptom management.

Supervision of the Lay Health Worker

The community health worker will be supervised by the RN at the Unite Here Health Fund offices in Chicago and Atlantic City. The RN will ensure that the protocol is carried out correctly and address any issues that may arise in the LHWs’ workflow. The CHWs at each site (2 0.4 FTE in Chicago, 3 0.3 FTE in Atlantic City) will participate in monthly meetings with the rest of the project members (at both Stanford and UHH) to review study accrual and program goals. At

these meetings, the RN will be responsible for providing a report on project progress and project issues incorporating feedback from the LHWs.

Quality of Life Measures

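### The removal rule lets a family's withdrawal take a consenting intervention-arm patient out of the study, and does not separate ending community health worker contact from ending data collection

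*Combined protocol and SAP*

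**What the plan says.** Protocol 3.2, under removal criteria, gives the only withdrawal rule in the text supplied: "Any patients or families of patients in the intervention arm who withdraw consent will be removed from the study". The next sentence gives its single stated consequence: "Upon removal, usual care will be restored for these patients".

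Other sections bear on how this would be read:

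- **Consent.** Protocol 3.1 describes the patient's consent only: "If a patient is interested and consents verbally" opens the enrolment step, and "Patients who refuse participation or have no capacity for decision-making or consent will not be included in the study". No family consent is described.
- **Family role.** Protocol 4.0 has the CHW meet "family and caregivers at the same time intervals where possible". This is part of the intervention.
- **Usual care.** Protocol 3.1 says: "The intervention will be provided in addition to the usual care processes". Usual care is therefore never suspended.
- **Data collection.** Protocol 3.3: "Data collection will occur at baseline and months 4 and months 12 for each patient in the study". Protocol 4.0: "All patients, throughout the study, will be asked to complete three surveys". Protocol 4.0 also lets a patient decline a survey that causes discomfort, without mentioning removal.
- **Analysis set.** Protocol 5.2 and SAP 4.2 include every patient, as randomised, under intention to treat. Neither mentions removed patients or the data they gave before removal.

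**The concern.** The rule tells site staff what to do, and they act on it months before anyone runs the analysis. If removal from the study is taken at its word, a patient whose family wants no more CHW meetings, or who personally wants to end CHW contact, gets no 4-month FACT-G. Some of these patients would still have answered.

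The primary contrast is the between-arm difference in 4-month change in FACT-G. Loss that depends on outcome and differs by arm biases it, and a family route open in one arm only is one way for loss to differ. The direction cannot be predicted: leavers may be sicker, or may be well and see no need for a CHW. The exploratory outcomes in the last 30 days of life (SAP 1.1.2) could also lose patients if families withdraw late in the illness.

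**Working it through.** **Reading the sections together**

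1. *Who triggers removal.* Patients or families. The phrase about the intervention arm may qualify both, or families only. On either reading the family route exists only in that arm.
2. *Whose consent.* Only the patient consents under Protocol 3.1, so the text does not say what a family withdraws. Yet the patient is the one removed.
3. *What ends.* The stated consequence is a return to usual care. Since usual care runs alongside the intervention, this describes only the end of the CHW add-on. The stated action, removal from the study, is wider.
4. *Whether data collection continues.* Protocol 3.3 and 4.0 schedule surveys, and claims extraction, for patients in the study. Whether a removed patient still counts is not stated.

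**Size**

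The plan gives no figure for withdrawal, so there is none to reproduce. Inputs from Protocol 5.1 and the SAP sample size paragraph: 80 per arm, SD of change 9.5, target difference 4, within-subject correlation 0.8.

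Standard error of the contrast = 9.5 × √(2/80) = 1.50 points.

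Let p1 and p0 be the shares lost in the intervention and usual-care arms. Let D be how many points less leavers would have changed than stayers, taken as equal in both arms. In each arm the stayers' mean exceeds the full-arm mean by p × D. If all rows of leavers are dropped:

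bias = (p1 − p0) × D

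The values of p and D are assumptions; no document supplies them.

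| Loss, intervention vs usual care | D = 4 | D = 8 |
|---|---|---|
| 5% vs 0% | 0.05 × 4 = 0.2 | 0.05 × 8 = 0.4 |
| 15% vs 10% | 0.05 × 4 = 0.2 | 0.05 × 8 = 0.4 |
| random loss | 0 | 0 |

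The second row shows that loss common to both arms cancels when D is the same, so the excess is what counts. If leavers would have changed more than stayers, the signs reverse.

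Against the standard error: 0.2/1.50 = 0.13 and 0.4/1.50 = 0.27.

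The planned GEE would keep leavers' baseline rows, which reduces the bias slightly. In a simulation of that model (per-visit SD 9.5/√(2 × (1 − 0.8)) = 15.02, exchangeable correlation 0.8, no true effect, 5% vs 0% loss), the 4-month bias was 0.17 points for D = 4 and 0.36 for D = 8. The two-degree-of-freedom interaction test rejected in 5.3% and 5.9% of trials, against 5.3% with no loss (Monte Carlo error about 0.3 percentage points).

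*Sensitivity to the SD.* If 9.5 were the SD of a single score, the SD of change would be 9.5 × √(2 × (1 − 0.8)) = 6.01 and the standard error 0.95. The same biases would then be 0.2/0.95 = 0.21 and 0.4/0.95 = 0.42 standard errors.

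**The case against.** **Intention to treat already covers this.** Protocol 5.2 and SAP 4.2 are universal and make no exception for removed patients, and stopping follow-up after consent is withdrawn does not contradict them. That stands. A reader might infer that the rule violates intention to treat, and the documents do not support so much. But the principle defines who is analysed; it does not create a 4-month survey that staff were told not to collect.

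**Usual-care patients may be covered.** If the arm qualifier attaches to families only, the rule applies to any patient in either arm. That stands too. A reader might infer that the usual-care arm has no withdrawal rule. The sentence is ambiguous on this; only the family route is clearly confined to one arm.

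**The harm may be small.** Patients who withdraw their own consent to data collection are lost under any wording. Only two groups could be retained: those whose family withdraws while their own consent stands, and those who end CHW contact but would still give data. The documents size neither group. A reader might take a severe case, such as 20% vs 0% loss with D = 8 (bias about 1.4 points under the planned GEE), as the effect of this rule. That case models all outcome-linked loss, assumes none under usual care, and sets D at twice the design difference. None of this has a source in the documents.

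**The consent text may settle it.** Consent pages and appendices were not available, so they may separate withdrawal from contact and withdrawal from data. This limits the point to what Protocol 3.2 says and to its missing link with the analysis sections.

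**Conclusion.** The point holds as a defect in an operative rule. As written, Protocol 3.2 can remove a patient whose own consent stands, by a route open in one arm only, and can end data collection when only CHW contact was meant to end. The loss would be avoidable, and the analysis could not recover it.

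Its size is unknown. With a 5% excess loss and leavers 4 to 8 points worse, both assumed, the bias is about 0.2 to 0.4 points against a standard error of about 1.5, and the false-positive rate stays close to nominal. It grows with the excess loss and with D, vanishes if loss is random, and may go in either direction. Only the avoidable part is due to this rule. The case for change rests on low cost and on follow-up that cannot be recovered later, not on a demonstrated large bias: a cheap improvement.

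**What to change.** 1. **Amend Protocol 3.2 with one rule for both arms.** Ending CHW contact, or a family's withdrawal while the patient's own consent stands, does not by itself end study participation. Such patients stay in their randomised arm for the 4- and 12-month surveys, chart abstraction and claims, unless the patient (or a legally authorised representative if capacity is lost) withdraws consent to data collection. This concerns data collection only and sets no rule on when CHW contact stops.
2. **State in Protocol 3.2, Protocol 5.2 and SAP 4.2** that data collected before withdrawal stay in the intention-to-treat analysis as far as consent allows.

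If the type of withdrawal is logged, the log can reveal the arm and must be kept from blinded staff. Before choosing who holds it, reconcile Protocol 4.0, which names the local site coordinator as knowing the assignment, with SAP 2.5, which lists only the community or lay health workers as unblinded.

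**Cost.** A one-paragraph amendment, matching consent wording, one or two SAP sentences and a few survey contacts: at 5% of 80, 4 patients × 2 visits = 8 at most. Patients who withdraw consent to data collection remain missing, so the change reduces the loss without removing it, and does not by itself equalise loss between arms.

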3.3 Enrollment

The target number of subjects at the site is 160 (80 per arm). Patient enrollment will continue until sample size is reached (anticipated 24 months). Data collection will occur at baseline and months 4 and months 12 for each patient in the study. The data follow-up period (to assess utilization) will occur for up to 12 months following each patient enrollment or death (whichever is first).

4.0 MATERIALS AND METHODS

After a patient is enrolled in the study, the patient will be registered and entered into the project database (CarMa) and assigned an identification number. The identification number will be used on all subject-specific documents and research-related forms.

During registration, patients will be randomized to two arms (Arm A: Usual Care or Arm B: LEAPS Intervention). Specifically, the patients will be randomized 1:1 using a simple randomization strategy in each site into two arms at each site.

All patients, throughout the study, will be asked to complete three surveys: 1) patient health-related quality of life (using Functional Assessment of Cancer Therapy – General (FACT-G) and 2) satisfaction with decision-making (Satisfaction with Decision Scale) and 3) the patient activation measure (Patient Activation Measure-13). A trained study staff member will administer the surveys at baseline (month 0) and again at 4 months and 12 months for patients in the intervention and usual care arm. Participant information will be entered into the CarMa database within 7 calendar days. Study team members will conduct electronic health record chart review of each participant and abstract date of the following: goals of care documented by oncology clinician, advance directive, and Physician Order for Life Sustaining Treatment. All health care claims data will be provided by UHH to the study team for each participant in the study at the study end which will consist of all charges and paid claims for total costs including outpatient, inpatient and pharmacy services. All study team members will be blinded to the randomization assignment. Only the community health workers will know the study assignment and the local site coordinator at each site.

As part of usual care, study PI and team members redesigned benefits such that any member of UHH with cancer will also receive waived copays if they choose to seek care at the preferred

provider in Atlantic City. We will also provide each member with access to transportation and other services to receive care at the preferred provider.

- Arm A: Usual Care (Control) / No Intervention

Patients in this arm receive “usual” care coordination from their care coordination team which includes case management by a registered nurse practitioner to address financial concerns, care navigation and coordination.

- Arm B: LEAPS/ Intervention Group

The intervention will be comprised of a CHW assignment with a baseline introduction (either telephonic or in-person) of the program followed by a visit (telephonic or in-person) with the community health worker to screen for health-related social needs, identify and refer to community resources for any identified complication from social determinants of health and to begin intervention regarding goals of care and symptom management. All CHWs have undergone standardized training with additional supervised visits to gain skills in engaging patients and families in goals discussion and in symptom assessment algorithms (see Appendix for Details).

The CHW will contact patients based on patients’ ongoing needs but will provide at a minimum weekly support from time to enrollment up to 4 months post-enrollment and then monthly from 4-months post-enrollment until 12-months post-enrollment. The CHW will also conduct meetings with patient’s family and caregivers at the same time intervals where possible. The intervention details are provided in the Appendix.

Lay Health Worker Training

The PI and UHH staff provide ongoing training for the CHWs through formal classroom training (See Appendix for a list of topics covered), biweekly case rounds, shadowing and role plays. All CHWs will also be provided with previously tested and developed standardized training manuals that are refined based on feedback from stakeholders at UHH. The manuals include a highly detailed workflow of the project, from enrollment to completion. CHWs also will receive training on what to say during patient contact, advanced care planning conversations, documentation of advance care planning, the study calendar, data management, and key contact information. CHWs will also receive training on symptom management.

Supervision of the Lay Health Worker

The community health worker will be supervised by the RN at the Unite Here Health Fund offices in Chicago and Atlantic City. The RN will ensure that the protocol is carried out correctly and address any issues that may arise in the LHWs’ workflow. The CHWs at each site (2 0.4 FTE in Chicago, 3 0.3 FTE in Atlantic City) will participate in monthly meetings with the rest of the project members (at both Stanford and UHH) to review study accrual and program goals. At

these meetings, the RN will be responsible for providing a report on project progress and project issues incorporating feedback from the LHWs.

Quality of Life Measures

The FACT-G is a quick, validated, 27- item compilation to assess QOL domains with discriminate ability and sensitive to changes in QOL over time.

The Satisfaction with Decision scale is a quick, validated 6-question survey to assess patient experiences with decision-making.

The Patient Activation Measure is a validated measure used to assess patient activation.

[name] has used these measures with success in a similar project completed at the Palo Alto Veterans Hospital (Palo Alto, CA). Unite Here Health uses Patient Activation Measure as part of usual care at their organization.

If patients feel discomfort while conducting their surveys, they may choose to not complete them. If there are any psychological events that occur during the study, these will be reported to the site PI.

Site PI: [name]/[name]

[name]/[name] are responsible for overall study supervision as well as the following:

Conducting biweekly meetings with all study staff members, troubleshooting recruitment and follow-up challenges, participating in the training of the CHWs, ensuring proper data collection, and general upkeep. The site PI is also responsible for interacting with the protocol director at Stanford, [name]. As this is [name] conception, and she piloted at another site, she will be able to provide [name]/[name] with specific advice and recommendations should challenges arise.

Protocol Director: [name]

[name], PI of the study, is responsible for the overall study including corresponding with the site PI to help troubleshoot any challenges in data collection or follow-up. [name] is also responsible for assisting the sites in implementing the intervention, following study protocols, and responsible for conducting and overseeing data analysis and manuscript publication.

